Protocol: The influence of cognitive behavioural therapy for insomnia on self-reported endocrine therapy adherence: a mixed methods pilot study

University of Strathclyde: UEC23/09

Document date: 20/02/2023

1. Introduction

Breast cancer (BC) is the most common type of cancer in the UK, and the highest cause of cancer-related death in women(1). Approximately 70% of BC cases are hormone-receptor positive, which means the cancer cells grow in response to hormones oestrogen and/or progesterone. Following primary treatment (usually surgery, chemotherapy and/or radiotherapy), these cases are treatable with endocrine therapy. This is prescribed in the form of daily tablets for 5-10 years. This treatment works by either reducing the volume of oestrogen produced in the body (Aromatase inhibitors) or preventing oestrogen from binding to its receptors (Tamoxifen) (2).

When it is taken as prescribed, endocrine therapy is successful in reducing the risk of breast cancer recurrence and mortality. Tamoxifen can reduce the risk of recurrence by up to 50%, and aromatase inhibitors can reduce the chance of recurrence by a further third in comparison(3). Despite the clinical advantages of ET, compliance with this medication is often not optimal. Research indicates that up to half of those prescribed ET take their medication less than 70% of the time(4). This reflects suboptimal adherence (the extent to which patients take the medication as prescribed) and persistence (the duration of medication use, from initiation to discontinuation) (Wasserman et al., 2017). Nonadherence and nonpersistence are related to increased risk of BC recurrence and mortality(5). Therefore, to further improve BC outcomes, adherence to this medication should be maximised.

Predictors of ET adherence include younger and older age, switching ET medication type, comorbidities, and out of pocket medication costs(6). Another major factor which makes adherence challenging is side effects, which have severe impacts on quality of life and sense of identity and returning to normality after cancer treatment(7,8). These recent studies indicate that side effects may present a means of improving adherence as BC survivors express a desire for support in managing them, and they are amenable to improvement than demographic and clinical predictors.

One side effect which may present an appropriate target is insomnia. Characterised by difficulty falling and staying asleep, insomnia common in cancer patients and especially among those diagnosed with BC(9). This is debilitating to carrying out daily activities and has further effects on mental health and ability to move on from BC treatment(8). Importantly, sleep problems are influenced by other treatment side effects such as hot flashes, night sweats, and musculoskeletal pain, and related to depression and anxiety in BC survivors(10,11). Insomnia is therefore a transdiagnostic symptom with the potential to

reduce the burden of several different ET side effects and overall quality of life. Unlike hot flashes and pain, sleep can be treated non-pharmacologically using cognitive behavioural therapy, which is considered the gold standard treatment for insomnia (12). This has been found to improve not only insomnia symptoms but also depression, anxiety, and fatigue in BC survivors(13), and can be delivered efficiently to groups of people and treat these symptoms non-pharmacologically(14,15).

Thus far, interventions to improve ET adherence have focused on patient education and reminders to take medication, which have had little success in improving adherence (Ekinci et al., 2018; Heiney et al., 2019). Recent protocols include components of side effect management(16), which addresses research finding that BC survivors express a desire for support and willingness to try new strategies with the aim of better side effect management (7,8). However, to the best of our knowledge, there have been no attempts to improve adherence by targeting a specific ET side effect. Sleep may present an opportunity here as it is a transdiagnostic target which is highly prevalent in this population, and can be effectively treated non-pharmacologically using CBT-I.

This study will utilise a randomised, waitlist-controlled design. We will aim to recruit 40 BC survivors who experience sleep problems and struggle to take their ET medication as prescribed. The main objective of this study is to explore the effect of CBT-I (delivered through videoconferencing) on sleep problems and adherence to ET in BC survivors.

2. Methods

2.1. Design

The study is a randomised, waitlist-controlled trial of CBT-I. The advantages of a waitlist control group are: this ensures all participants have the opportunity to receive the recommended treatment for insomnia, and that by utilising control participants as intervention participants after their participation in the control condition, we can increase the statistical power of the study. The immediate intervention group will complete assessments at baseline, post-intervention (approximately 4 weeks after baseline), and after a further 8 weeks (12 weeks post-randomisation follow-up). The waitlist group will complete these assessments at the same timepoints, then 2 additional assessments after they receive the intervention, and after a further 8 weeks. The study is expected to take approximately 12 weeks from baseline

to completion (follow-up assessment). This study has been granted ethical approval has been granted from the University of Strathclyde ethics committee (UEC23/09).

2.2. Participants

Participants will include BC survivors who: experience symptoms of insomnia, self-report to be nonadherent to their ET medication, are fluent in English, and have access to videoconferencing software. Treatment nonadherence and insomnia symptoms will be established first during the screening interview, and at baseline, by responses to the Medication Adherence Report Scale (MARS-5) and Sleep Condition Indicator (SCI), respectively, using established cut-off scores.

Exclusion criteria include: individuals who are currently pregnant or breastfeeding, have received CBT-I within the past 12 months, have received chemotherapy or radiotherapy within the past 4 weeks or have plans for future treatment, struggle with substance misuse, or have an unstable physical or mental health condition (e.g. psychosis) which would be incompatible with CBT-I treatment.

Participants will not be excluded on the basis of other sleep disorders, if they report that these are stable and well-managed. Participants will not be excluded on the basis of a palliative BC treatment plan. However, during the screening interview the nature of CBT-I treatment will be explained to them, as this treatment can be difficult to implement, and they will be asked if they feel well enough to participate.

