2.2.1. Recruitment

We will aim to recruit a sample of 40 participants. A-priori power analysis was conducted using G*Power version 3.1.9.7 (Faul et al., 2007) to determine the minimum sample size required to test the study hypothesis using a repeated measures ANOVA (within-between interaction). Results indicated the required sample size to achieve 80% power for detecting a medium effect (significance criterion α =.05) was *N*=18. Therefore, the target sample size of *N*=40 is adequate to test the study hypothesis.

Recruitment will involve emailing participants of a previous study (UEC21/29) who indicated that they would be interested in participation in future research studies. We will contact individuals from this sample whose responses indicated they are nonadherent to their ET medication and experience significant sleep problems, informing them of the opportunity to take part in this study.

The initial email will briefly outline the nature of the study and include an information sheet with full study details. Those who are interested will be asked to respond to this initial email so that a screening interview can be scheduled.

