2.3. Procedure

Those who indicate interest in participation will be emailed a link to a virtual consent form via Qualtrics survey platform. Following informed consent, a screening interview will be scheduled. They will then be interviewed to ensure eligibility criteria are met. Screening interviews will be carried out by the PhD student: if there are any points of uncertainty, clarification will be sought through discussion with academic supervisors. Those who meet inclusion criteria following screening will be sent a link to the baseline assessment, then randomised to either the intervention or waitlist control group. All further assessments will be sent via email and carried out through Qualtrics survey platform.

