2.7 Analytic approach

Participants demographics and clinical characteristics will first be presented. Descriptive data will be presented for each outcome measure (MARS-5, SCI, GAD-7, PHQ-9, FFS and BESS subscales) and sleep diary variables at each of the 3 timepoints (baseline, post-intervention, and 12-week follow-up).

Hypotheses will be tested using a 2x3 mixed factorial ANOVA. Between-subjects factor will be group (intervention or control), and within-subjects factor will be timepoint (baseline, post-intervention, and 12-week follow-up). We will examine the main effect of group, timepoint and interaction of group and timepoint. If a significant main effect is found, subsequent comparisons will be made applying Bonferroni correction.

3. Discussion

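### Section 2.7 uses no pre-randomisation score as a covariate, and leaves out the screening MARS-5 and SCI readings that section 2.2 indicates are taken; ANCOVA on these scores would sharpen the arm comparison

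*Combined protocol and SAP*

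**What the plan says.** Section 2.2 (Participants) says that the two entry conditions, nonadherence and insomnia, "will be established first during the screening interview, and at baseline, by responses to the Medication Adherence Report Scale (MARS-5"). For insomnia the scale named is the SCI, and each of the two scales is read against an accepted threshold. Section 2.3 (Procedure) gives the order: women who pass the screening interview "will be sent a link to the baseline assessment, then randomised to either the intervention or waitlist control group". Anything scored at screening or at baseline is therefore scored before allocation.

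Section 2.7 (Analytic approach) states: "Hypotheses will be tested using a 2x3 mixed factorial ANOVA". The "within-subjects factor will be timepoint (baseline, post-intervention, and 12-week follow-up". No covariate is named, and the screening score has no role. Nowhere else in the document does it serve any purpose but eligibility.

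MARS-5 is the primary outcome (section 2.6.1). SCI, a secondary outcome (section 2.6.2), measures the sleep problem named in the main objective.

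**The concern.** A five-item self-report is a noisy measure, and the trial is small: "We will aim to recruit a sample of 40 participants". Section 2.4 allocates 2:1 to waitlist or intervention, which as worded is about 27 and 13. The width of the interval for the arm difference will limit what this pilot can say.

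Scores taken before randomisation can explain part of the variation between women at follow-up without biasing the comparison of arms. The plan appears to collect two such scores on each of the two key scales. It uses one of them as an outcome level, which is a less efficient use than as a covariate, and does not use the other.

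**Working it through.** **The plan's own figure.** Section 2.2.1 gives N=18 as the "required sample size to achieve 80% power for detecting a medium effect (significance criterion α =.05"), for a "repeated measures ANOVA (within-between interaction"). Taking medium as f = 0.25 (an assumption), with 2 groups, 3 timepoints and sphericity, the noncentrality is f² × N × 3/(1 − rho), on 2 and 2(N − 2) degrees of freedom.

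- rho = 0.5, N = 18: 0.0625 × 18 × 3/0.5 = 6.75 on 2 and 32 df, power about 59%. The N needed for 80% is 28.
- rho = 0.7, N = 18: 0.0625 × 18 × 3/0.3 = 11.25, power 82%.

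So 18 is not reproduced from the stated inputs, though an unstated correlation near 0.7 would explain it. Nothing below depends on this figure.

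**Inputs.** N = 40 and 2:1 allocation come from sections 2.2.1 and 2.4. Two quantities are not in the documents and are assumed: rho, the correlation of a pre-randomisation score with follow-up, and r12, the correlation between the screening and baseline readings. Data are taken as complete, with equal variances.

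**Variance of the arm contrast at one follow-up, per person, in units of the outcome variance.**

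- Change from baseline, the component of the planned ANOVA interaction that compares arms: 2(1 − rho)
- ANCOVA on baseline alone: 1 − rho²
- ANCOVA on both readings, if each correlates rho with follow-up (mean, or both entered): 1 − 2rho²/(1 + r12)

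| rho | change | ANCOVA, one reading | both, r12 = rho | further cut | both, r12 = 0.9 | further cut |
|---|---|---|---|---|---|---|
| 0.3 | 1.40 | 0.91 | 0.862 | 5% | 0.905 | 0.5% |
| 0.5 | 1.00 | 0.75 | 0.667 | 11% | 0.737 | 2% |
| 0.7 | 0.60 | 0.51 | 0.424 | 17% | 0.484 | 5% |

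At rho 0.5, for example, 1 − 2 × 0.25/1.5 = 0.667 and 1 − 2 × 0.25/1.9 = 0.737. The ANCOVA step supplies most of the gain at rho 0.5. At rho 0.7 with r12 = 0.7 the two steps are about equal (0.09 each).

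**Power** for a 0.5 SD difference at 27:13 and rho 0.5, two-sided 5%: 30% for the change contrast, 38% for ANCOVA on one reading, 42% with both if r12 = 0.5, and 39% if r12 = 0.9. The last two count one covariate, that is, the mean of the readings.

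**Cost of estimating the extra coefficient.** With q normally distributed covariates, chance imbalance inflates the variance by 1 + q/(N − q − 3). At N = 40 this is 1 + 1/36 = 1.028 for one covariate and 1 + 2/35 = 1.057 for two. At rho 0.5, one reading gives 0.75 × 1.028 = 0.771. Both entered separately give 0.667 × 1.057 = 0.705 if r12 = 0.5, but 0.737 × 1.057 = 0.779 if r12 = 0.9, slightly worse than one reading.

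**Mean or separate scores.** Suppose baseline correlates 0.6 with follow-up, the interview score 0.4, and r12 = 0.5 (assumed).

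- Baseline alone: 1 − 0.36 = 0.640
- Mean of the two: 1 − 0.5²/0.75 = 0.667, worse than baseline alone
- Both entered: 1 − (0.36 + 0.16 − 2 × 0.6 × 0.4 × 0.5)/(1 − 0.25) = 0.627

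**Entry cut-offs.** Simulated selection on SCI of 16 or below (assumed mean 12 to 20, SD 6, unselected rho 0.5 to 0.8 with r12 equal to rho) left a further cut from the second reading of about 4% to 16% under ANCOVA.

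**The case against.** The strongest objection is to the premise. Section 2.2 can also be read as status established by interview first and by scale responses only at baseline. Section 2.3 mentions an interview to check eligibility but names no scale, and section 2.1 lists assessments from baseline onward. No section says that numeric screening scores are kept. This stands in part: two scored readings is the more natural meaning, since cut-offs need scores, but retention of the scores is an inference.

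The second objection is that the gain is small and conditional. This stands. The 11% and 17% figures assume that the two readings agree no better than baseline and a follow-up 4 or 12 weeks later. Readings taken close together would usually agree better, and the interval between them is not stated. Even 11% and 17% narrow the interval by only about 6% and 9% (square roots of 0.667/0.75 and 0.424/0.51).

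Third, one baseline reading is ordinary practice. That also stands. A reader might infer that the planned ANOVA is biased or invalid; the documents do not support this, because a randomised comparison of change from a single baseline is sound. A reader might also infer that the screening score alone would recover 8% to 17% of the variance against the plan as written. It would not: over assumed correlations of 0.4 to 0.7, those figures are measured against single-baseline ANCOVA, which the plan does not use.

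That the screening score was used for selection is not an objection to its use as a covariate, because both arms were selected alike before allocation.

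**Conclusion.** The point holds as an optional improvement in efficiency, not as a defect of validity. Over the assumed range of rho from 0.3 to 0.7, adjusting for pre-randomisation scores gives a lower variance than the planned baseline-to-follow-up contrast. At rho 0.5 it falls from 1.00 to between 0.67 and 0.74 with both readings, and 0.75 of that is reached with the baseline score alone. The second reading adds from near zero to about 11% at rho 0.5, or 17% at rho 0.7, depending on how closely screening and baseline agree.

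These sizes rest on assumed correlations and complete data, and on the inference that screening scores are numeric and kept. If they are not, the case for ANCOVA on baseline remains and the case for the second reading falls away.

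**What to change.** In section 2.7, estimate the between-arm difference in MARS-5 and in SCI at post-intervention and at 12 weeks by ANCOVA, or by a mixed model of the two post-baseline timepoints. Use the baseline and screening scores as covariates. Enter them separately, because an interview and an online survey may predict follow-up unequally; use their mean only if they are judged interchangeable. Fix the choice before outcome data are seen.

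Do not average the screening score into the baseline level of the ANOVA. It was used for selection, so regression to the mean would distort the time effect and the within-group changes.

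State that numeric screening scores are retained. Reconcile section 2.2, where eligibility is established at both points, with section 2.3, where it is settled before the baseline link is sent. Before any of this, correct section 2.6.1: it gives a summed total of 1-5, but five items each scored 1 to 5 sum to 5 × 1 = 5 up to 5 × 5 = 25.

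The cost is that the main model in 2.7 is replaced, and that entering both scores uses one more degree of freedom, which can cancel the extra gain if the readings agree very closely. If the scores are already recorded, no new data are needed.

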2.2.1. Recruitment

We will aim to recruit a sample of 40 participants. A-priori power analysis was conducted using G*Power version 3.1.9.7 (Faul et al., 2007) to determine the minimum sample size required to test the study hypothesis using a repeated measures ANOVA (within-between interaction). Results indicated the required sample size to achieve 80% power for detecting a medium effect (significance criterion α =.05) was *N*=18. Therefore, the target sample size of *N*=40 is adequate to test the study hypothesis.

Recruitment will involve emailing participants of a previous study (UEC21/29) who indicated that they would be interested in participation in future research studies. We will contact individuals from this sample whose responses indicated they are nonadherent to their ET medication and experience significant sleep problems, informing them of the opportunity to take part in this study.

The initial email will briefly outline the nature of the study and include an information sheet with full study details. Those who are interested will be asked to respond to this initial email so that a screening interview can be scheduled.

2.3. Procedure

Those who indicate interest in participation will be emailed a link to a virtual consent form via Qualtrics survey platform. Following informed consent, a screening interview will be scheduled. They will then be interviewed to ensure eligibility criteria are met. Screening interviews will be carried out by the PhD student: if there are any points of uncertainty, clarification will be sought through discussion with academic supervisors. Those who meet inclusion criteria following screening will be sent a link to the baseline assessment, then randomised to either the intervention or waitlist control group. All further assessments will be sent via email and carried out through Qualtrics survey platform.

2.4. Randomisation

Participants will be allocated on a 2:1 basis to the waitlist or intervention group. The study team will have no influence over the randomisation process. Participants will be randomised using block randomisation in blocks of 10. The advantage of this method is that it maintains balance between intervention and control group, as significant imbalance would reduce the power of the study in a small sample (Lim & In, 2019; Pinto et al., 2022).

Upon providing informed consent, participants will be assigned a unique identifier (UID). A PhD student unrelated to the study will be given a list of these UIDs and use an online randomisation tool to generate an allocation sequence, which will be used to assign each group's participants. They will then pass the list of UIDs assigned to each group to the PhD student for the study, who will establish which participants are in each group. Following randomisation, the intervention group will be emailed a recurring link to access CBT-I sessions via videoconferencing.

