transdiagnostic side effect which may present an appropriate target for intervention to relieve overall side effect burden and improve ET adherence. CBT-I is considered the gold standard gold-standard treatment for insomnia (Ma et al., 2021), and has been effective in this population before in reducing not only sleep, but also depression, anxiety, and fatigue (D'arico et al., 2016).

The current study will administer CBT-I in groups of approximately 5 participants, through videoconferencing. A recent meta-analysis found no significant difference between remotelydelivered and conventional face-to-face CBT-I and reported that remotely-delivered CBT-I may be slightly more efficacious in comparison to in-person treatment (Ma et al., 2021). This format also has the advantage of widening accessibility, removing the financial and practical burden of travelling to in-person sessions. Delivering the intervention using a group (rather than individual) format presents a time-efficient and cost-effective intervention (Garland et al., 2022), and also addresses preferences expressed by BC patients to receive support with side effects in a group setting, so that they can learn from their peers' experiences (Jacobs et al., 2020). Despite being the gold-standard treatment for insomnia, clinician and patient-level barriers have limited access to this intervention (Koffel et al., 2018; Savard et al., 2021). The mode of delivery utilised in the current study therefore widens accessibility of the intervention. Furthermore, A recent systematic review by Peddie et al. (2021) reported that BC survivors showed high motivation to continue treatment, and willingness to make lifestyle changes to reduce the burden of side effects and persevere with ET. This willingness to try different strategies to reduce side effect burden indicates that they may be receptive to behavioural intervention such as CBT-I.

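### The 2:1 allocation to waitlist conflicts with the plan's own balance-for-power rationale and its blocks of 10, at a modest cost in efficiency and with no reason given

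*Combined protocol and SAP*

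**What the plan says.** Section 2.4 fixes the ratio: "Participants will be allocated on a 2:1 basis to the waitlist or intervention group". Read literally, two women go to the waitlist for each woman who starts CBT-I at once. It then fixes the method: "Participants will be randomised using block randomisation in blocks of 10". The reason given for the method is that "it maintains balance between intervention and control group, as significant imbalance would reduce the power of the study in a small sample".

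Three other sections bear on the point.

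- **Section 2.2.1 (Recruitment):** "We will aim to recruit a sample of 40 participants". The power calculation is for the within-between interaction of a repeated measures ANOVA at α = .05 and gives N = 18. It does not mention unequal allocation.
- **Sections 2.1 (Design) and 2.5 (Intervention):** waitlisted women receive CBT-I after their 12-week assessment, which then serves as a new baseline. Section 2.1 says that using them again in this way raises power.
- **Section 3.1 (Study strengths and limitations):** "The current study will administer CBT-I in groups of approximately 5 participants, through videoconferencing".

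Section 2.7 (Analytic approach) specifies one analysis, a 2x3 mixed ANOVA on group and the three common timepoints. It does not use data collected after the waitlist group crosses over.

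**The concern.** The paragraph warns that imbalance between arms costs power in a small sample, and it also builds such an imbalance into the ratio. No section explains the ratio. The block size does not fit it either: 10 is not a multiple of 3, so each block must depart from 2:1, and the plan does not say how blocks are to be filled.

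What is at stake is the precision of the only randomised comparison of CBT-I with no CBT-I on adherence. Under 2:1, about 13 of the 40 women supply the treated side of that comparison. About 27 wait until after week 12, against 20 under 1:1. Whoever generates the sequence also has to guess the composition of each block.

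**Working it through.** **Inputs.** From the documents: N = 40, ratio 2:1, block size 10, two groups, three timepoints, α = .05, 80% power, a medium effect, stated requirement N = 18. Assumed, because the documents do not give them: Cohen's f = 0.25 for a medium effect, the within-person correlation ρ, sphericity, and the ratio of the SDs of change in the two arms.

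**1. The plan's own figure.** For the interaction with k = 2 groups and m = 3 timepoints, λ = f²·N·m/(1 − ρ), with df (k − 1)(m − 1) = 2 and (N − k)(m − 1).

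- ρ = 0.7, N = 18: λ = 0.0625 × 18 × 3/0.3 = 11.25 on 2 and 32 df; power 82.5%.
- ρ = 0.5, N = 18: λ = 0.0625 × 18 × 3/0.5 = 6.75; power 59.5%. Here N = 28 is needed.

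So 18 is reproduced with ρ = 0.7, a value that the plan does not state. The point about the ratio does not depend on it.

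**2. Information in the randomised comparison, equal variances.** The equally allocated equivalent of arms n₁ and n₂ is 4/(1/n₁ + 1/n₂) = 4n₁n₂/(n₁ + n₂).

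| Split (waitlist:CBT-I) | Equivalent N | Standard error against 20:20 |
|---|---|---|
| 20:20 | 40.0 | 1.000 |
| exact 2:1 | 40 × 8/9 = 35.6 | 1.061 |
| 27:13 | 4 × 27 × 13/40 = 35.1 | 1.068 |
| 26:14 | 36.4 | 1.048 |
| 28:12 (each block 7:3) | 33.6 | 1.091 |
| 24:16 (each block 6:4) | 38.4 | 1.021 |

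The last two rows show the spread if every block of 10 is filled in the same way, at one or other of the two splits nearest to 2:1.

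**3. Power on the planned test at N = 40, f = 0.25.** Multiply λ by 8/9 for 2:1; df are 2 and 76.

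- ρ = 0.5: λ = 15.0 at 1:1 and 13.3 at 2:1; power 93.5% and 90.4%.
- ρ = 0.7: λ = 25.0 and 22.2; power 99.5% and 99.0%.

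The loss is about 0.5 to 3 points.

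**4. A simpler comparison, for scale only.** For a two-sample t-test on change (two-sided 5%, 38 df), which the plan does not specify, power at a difference of 0.9 SD is 79.2% at 20:20 and 73.8% at 27:13. The difference detectable with 80% power is 0.91 SD and 0.97 SD.

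**5. Unequal variances.** Let r be the SD of change in the CBT-I arm divided by that in the waitlist arm. The efficiency of 27:13 relative to 20:20 is (r²/20 + 1/20)/(r²/13 + 1/27).

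- r = 1: 0.1000/0.1140 = 0.88, a 12% loss.
- r = 1.5: 0.1625/0.2101 = 0.77, a 23% loss.
- r = 0.67: 0.0724/0.0716 = 1.01, no loss.

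**6. Fit with the other design numbers.** At 1:1, 40 women make four blocks of 10, each 5:5, giving 20 per arm and therapy groups of 5. At 2:1, about 13 women start at once, so 13/5 is about three early groups; at 1:1, 20/5 is four.

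**The case against.** The strongest reply is that the loss is small and may buy something. On the test used to size the trial, power at N = 40 stays at 90% or above in both cases computed, and 35 equivalent women exceeds the stated requirement of 18. That stands, and it sets the weight of the point.

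A larger waitlist could also be deliberate. Those women supply control data first and within-person treatment data later, and Section 2.1 says this raises power. One student delivers all the therapy, so fewer early groups would ease the initial load. Both are plausible reasons, but the protocol gives neither as the reason for 2:1, and Section 2.7 does not analyse the post-crossover data.

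Balance could be read as holding the planned ratio against chance drift. That is arguable, but the sentence speaks of balance between the two groups and of imbalance costing power, and blocks of 10 would not hold 2:1 exactly in any case.

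Three stronger readings are tempting, and the documents do not support them.

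- **The ratio runs the wrong way because response varies more among treated women.** No SD ratio is given, and the direction is unknown. The primary outcome is bounded at the top, so scores in treated women could equally be compressed.
- **The pilot learns least about CBT-I.** Only the randomised contrast rests on about 13 treated women. All 40 are to be offered CBT-I, with assessments after it in both arms.
- **The information is lost for nothing.** The crossover data and early therapist load are possible returns, although unstated.

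**Conclusion.** The inconsistency in Section 2.4 is real: the ratio, the balance rationale and the block size do not fit together, and no reason for 2:1 is given. Blocks of 10, the balance wording and therapy groups of about 5 all fit 1:1, so 2:1 may be a drafting slip; the documents do not settle this.

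If 2:1 is carried out, the randomised comparison has the information of about 35 to 36 equally allocated women, assuming equal variances. On the planned interaction, the cost of 0.5 to 3 points of power assumes f = 0.25 and ρ between 0.5 and 0.7. If the SD of change differs between arms, the loss of information runs from none (ratio 0.67) to 23% (ratio 1.5).

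A reader might infer that the ratio leaves the trial underpowered. By its own N = 18 it does not. That figure needs ρ of about 0.7, but even at ρ = 0.5 the requirement of 28 lies below 35. The point is one of efficiency and consistency, worth correcting because the correction is cheap.

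**What to change.** Before the sequence is generated, replace 2:1 with 1:1 in Section 2.4 and state that each block of 10 holds five women per arm. The balance sentence can then stand, and each block fills one therapy group of about 5 in each arm.

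The amendment changes one ratio. Total recruitment and total CBT-I places are unchanged. The cost is about one more therapy group run early by the single student therapist instead of after week 12.

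If 2:1 is intended, for example for the crossover data or because of early therapist capacity, make three changes:

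- State the reason. If it is the crossover data, add to Section 2.7 the analysis that uses them.
- Use a block size divisible by 3. Because 40 is not a multiple of 3, the last block will be incomplete.
- Remove the sentence claiming balance for power.
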